## 7.4 Interim Analyses

The size of the trial is based upon the assumptions currently available and provides high power to detect what the Sponsor believes is the smallest clinically meaningful difference in OS under these assumptions. However, as there is uncertainty in the assumptions, interim analyses provides an opportunity to stop the trial early if the treatment benefit of cabozantinib is larger than expected, potentially allowing cabozantinib to become available sooner to this patient population.

Two interim analyses for primary endpoint of OS are planned. The interim analyses will be conducted at the time when approximately 311 and 466 deaths have been observed respectively. It is anticipated that this will be at approximately the 50% and 75% information fraction respectively for OS. Type I error for the interim analysis will be controlled by a Lan-DeMets O'Brien-Fleming alpha spending function as described in

Section 7.3. The actual critical values employed at the interim and final analyses of OS will depend upon the actual information fraction at the time of the interim analyses.

If the planned first or second interim OS analysis achieves overwhelming evidence of efficacy (p-value = 0.0031 or 0.0183, respectively, under trial design assumptions) in favor of cabozantinib, analyses of the secondary endpoints will be performed as planned. Interim analyses will be evaluated by the IDMC. Monitoring guidance will be provided to allow the study to be stopped early if the null hypothesis for OS is rejected in favor of cabozantinib. A nonbinding boundary for harm will be used by the IDMC to help evaluate subject safety. Stopping for futility is not planned.

## 7.5 Exploratory Efficacy Endpoints

Each exploratory endpoint will be analyzed using an appropriate two-sided statistical test without adjustment for multiplicity unless specified otherwise. Statistical results for exploratory endpoints will be considered descriptive. Exploratory analyses will be performed using all subjects in the ITT population unless specified otherwise.

## 7.5.1 Health-Related Quality of Life (HRQOL)

Health-related quality of life (HRQOL) will be assessed by the EuroQol Health questionnaire instrument (EQ-5D-5L). The questionnaire will be self-completed by the subjects at various time points until disease progression and will provide a generic measure of health for clinical appraisal (see protocol Section 5.5.8). The EQ-5D-5L questionnaire has two pages: a descriptive page which assesses on an increasing severity scale of 1-5 changes in the following five questions (dimensions): mobility, self-care, usual activities, pain/discomfort, and anxiety/depression. The second page has a 0-100 visual analogue scale (VAS) which records the subjects self-rated health between 100 (best health you can imagine) and 0 (worst health you can imagine) and serves as quantitative measure of health by the subject (see protocol Appendix F and EQ-5D-5L User Guide 2015).

To compare the two treatment arms the following summaries are planned at each time point for each of the 6 questions:

Within each treatment arm:

- Descriptive statistics (number of observations, mean and standard deviation)
- Rate of completion for the questionnaire at each time point. This is defined as total number of subjects who answered all questions on the EQ-5D-5L questionnaire / the expected total number of subjects still on study at the visit

- Mean change from baseline at each time point and the corresponding 95% CI and pvalue from one-sample t-test
- Effect size for change from baseline within arm, calculated as (mean of change in score/pooled standard deviation for baseline scores). An effect size greater than ≥ 0.3 will be considered potentially clinically meaningful
- Shift in the severity scale since baseline

#### Across treatment arms

- The difference in the effect sizes will be presented
- Difference in mean change from baseline for the questions at the time point will be evaluated by a two sample t-test
- Line plots for mean±standard error and the corresponding mean for change from baseline over time. Data from both treatment arms will be displayed on the same plot. In addition, these plots will also show the average state of the subjects at 3 landmark points, namely, around end of treatment, around progression and around 30 days post treatment follow-up for the two treatment arms
- Percentage of subjects in Level 1 (no problem) vs. Levels 2-5 (any problems) will be summarized over time
- Percentage of subjects with any problems (Level 2-5) will be compared between the treatment arms using a bar chart

The EQ-5D-5L may be converted into a single index (EQ-Index) value normalized across different countries where the index is validated. See Appendix D for conversion details. For EQ-VAS and EQ-Index, descriptive statistics for change from baseline at each time will be presented. Plots for mean $\pm$ standard error and mean change from baseline $\pm$ standard error over all time points for the two treatment arms will be generated. In addition, repeated-measures mixed-effects models will be used to explore treatment differences over time. These analyses will include the outcome variable of QOL score change from baseline. The predictors (fixed effects) will be the baseline scores, treatment arms, visit, and randomization strata described in Section 2.5. The individual subject nested within the planned treatment arm will be the random effect. All available data will be included for the analysis. The estimated least squares means for the two treatment arm and their difference, the p-values comparing the 2 treatment arms and the effect size will be presented. No adjustment will be made for multiple comparisons. An effect size of differences in the  $\geq$  0.3 range will be considered potentially clinically meaningful.

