### 4 GENERAL CONVENTIONS

The statistical principles applied in the design and planned analyses of this study are consistent with International Conference on Harmonization (ICH) E9 guidelines (ICH 1998).

Continuous data will be summarized using descriptive statistics (number of observations, mean, standard deviation, median, 25th and 75th percentiles, minimum, and maximum). Frequencies and percentages will be used for summarizing categorical (discrete) data.

Confidence intervals, when presented, will generally be constructed at the 95% level. For binomial variables, the normal approximation methods will be employed unless otherwise specified.

A month is operationally defined to be 30.4375 days. Six months is operationally defined to be 183 days.

All summaries will be presented by treatment arm unless otherwise specified.

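### The by-visit EQ-5D-5L arm comparisons are t-tests on change from baseline, without baseline or strata adjustment, and generally give up some precision

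*SAP*

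**What the plan says.** SAP 7.5.1 states that "the following summaries are planned at each time point for each of the 6 questions". The six questions are the five dimensions (mobility, self-care, usual activities, pain/discomfort, anxiety/depression) and the VAS. In the part of that section on comparisons across arms, the test is: "Difference in mean change from baseline for the questions at the time point will be evaluated by a two sample t-test". No covariate is named.

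The following paragraph turns to EQ-VAS and EQ-Index and adds that "repeated-measures mixed-effects models will be used to explore treatment differences over time". The outcome is change from baseline, and "The predictors (fixed effects) will be the baseline scores, treatment arms, visit, and randomization strata described in Section 2.5". No arm-by-visit term is listed. The SAP version history agrees on scope: it describes the repeated-measures analysis as added for those two measures.

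On status, SAP 7.5 says "Each exploratory endpoint will be analyzed using an appropriate two-sided statistical test without adjustment for multiplicity unless specified otherwise" and "Statistical results for exploratory endpoints will be considered descriptive".

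**The concern.** The same section adjusts for baseline and strata in one analysis and omits both in the other. For the five dimensions, the unadjusted t-test is the only between-arm test specified. For the VAS, it is the only one by visit, because a mixed model without an arm-by-visit term yields a single overall arm difference.

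A change score uses baseline with its coefficient fixed at 1, whereas ANCOVA estimates that coefficient from the data. When the true slope is not 1, the change score carries avoidable noise, and a chance baseline difference between arms is not fully removed. On a 1-to-5 item a subject starting at level 1 cannot improve, so change depends on where the subject began.

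At stake is how sharply each by-visit difference is estimated. This matters most at late visits with few subjects, where results will be read against the SAP's effect-size threshold of 0.3.

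**Working it through.** **Plan's own figure.** There is none to reproduce. The documents give no SD, correlation, power or interval width for any EQ-5D-5L comparison.

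**Inputs from the documents.** Planned arm sizes are 507 and 253 (SAP 2.4), the effect-size threshold is 0.3 (SAP 7.5.1) and the interval level is 95% (SAP 4).

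**Assumed.** The correlation r between baseline and follow-up, the ratio k of follow-up SD to baseline SD, and the share of subjects contributing at a late visit are all assumptions. SDs and slope are taken as the same in both arms.

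**Formulas, in baseline-SD units.**
- Variance of a change score: k² + 1 − 2rk.
- Residual variance under ANCOVA: k²(1 − r²).
- Difference between the two: (1 − rk)².

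The slope of follow-up on baseline is rk. In large samples the change score is therefore never more precise under these assumptions, and it is equally precise only when rk = 1.

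**Equal SDs (k = 1).** The SE ratio is √[2(1 − r)/(1 − r²)] = √[2/(1 + r)].

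| r | Change variance | ANCOVA variance | Excess SE of t-test |
|---|---|---|---|
| 0.3 | 1.40 | 0.91 | 24.0% |
| 0.5 | 1.00 | 0.75 | 15.5% |
| 0.7 | 0.60 | 0.51 | 8.5% |
| 0.9 | 0.20 | 0.19 | 2.6% |

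A simulation of 4,000 trials with 152 and 76 subjects gave 14.3% at r = 0.5 and 7.5% at r = 0.7, close to the formula.

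**Unequal SDs.**
- k = 1.2: excess 7.2% at r = 0.5 and 1.7% at r = 0.7.
- k = 1.5, r = 0.7: the slope is 1.05 and the excess is 0.1%.
- k = 0.8: excess between 26.2% and 41.1% for r from 0.3 to 0.9.

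**What this means for an interval (k = 1, r = 0.5).** The 95% half-width is 1.96 × √variance × √(1/n₁ + 1/n₀).
- All subjects, 507 and 253: √(1/507 + 1/253) = 0.0770. The half-width falls from 1.96 × 1.000 × 0.0770 = 0.151 to 1.96 × 0.866 × 0.0770 = 0.131 SD. Power at 0.3 SD goes from 97.4% to 99.4%.
- An assumed 30% at a late visit, about 152 and 76: the half-width falls from 0.275 to 0.239 SD. Power at 0.3 SD goes from 57% to 69%.
- The same late visit with r = 0.7: the half-width falls from 0.213 to 0.197 SD, and power goes from 79% to 85%.

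The gain is thus of little consequence early and more visible late. Protocol 3.2 expects an average of 3 to 5 months on treatment, so thin late visits are plausible, but the 30% is not a figure from the documents.

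**The case against.** The strongest reply is that nothing rests on this test. The results are descriptive and carry no alpha, and Protocol 1.4.2 frames the HRQOL aim as time to deterioration, not mean change by visit. That stands, and it limits the weight of the point.

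The SAP already gives EQ-VAS and EQ-Index a baseline- and strata-adjusted model, and EQ-Index is not among the six questions, so it gets no by-visit t-test. This narrows the gap to the five dimensions and the by-visit VAS contrasts. The plan also has shift summaries and any-problem percentages for the dimensions, but no other between-arm test for them. Linear ANCOVA on a 1-to-5 item is an approximation, as is a t-test on the same item.

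Several stronger readings are tempting and not supported:
- A reader might infer bias or a wrong type I error. With randomization and complete data the t-test is valid, because regression to the mean affects both arms equally in expectation.
- A reader might infer that baseline is ignored. It is used, with a fixed coefficient.
- A reader might expect narrower bars on the plots. These show mean ± SE, and a different between-arm test leaves them unchanged. The within-arm summary, "Mean change from baseline at each time point and the corresponding 95% CI", is likewise unaffected.
- A reader might quote the gain as a fixed sample-size equivalent. It depends on r and k, neither of which is given.

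Finally, the change has some cost. The strata form 3 × 2 × 2 = 12 cells, which may be sparse at late visits, and ANCOVA by visit still uses only subjects observed at that visit.

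**Conclusion.** The point holds as a low-impact matter of precision. The by-visit comparisons of the five dimensions and the VAS are unadjusted, although the baseline scores and strata are already collected and already used in the neighbouring model.

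With equal SDs assumed, the t-test's standard error is about 3% to 24% wider than that of ANCOVA for r from 0.9 to 0.3. The excess can be near zero when the slope is close to 1, and larger than 24% if follow-up SDs are smaller than baseline SDs. The comparison assumes a common slope and common SDs across arms. With 2:1 allocation, the large-sample ordering is not guaranteed if slopes differ by arm. No confirmatory conclusion of the trial is affected.

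**What to change.** Either of two changes to SAP 7.5.1 would do:

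1. Replace the by-visit t-test with ANCOVA of the score (or its change; the arm difference is identical once baseline is in the model) on arm, baseline score and the IxRS strata. Pre-specify a rule for collapsing or dropping sparse strata at late visits.
2. Add arm-by-visit and baseline-by-visit terms to the mixed model and extend it to the five dimensions.

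In both cases, report the adjusted by-visit difference with its 95% CI, in line with SAP 4 ("Confidence intervals, when presented, will generally be constructed at the 95% level"). Base the between-arm effect size on that difference, with the pooled baseline SD as the divisor, as SAP 7.5.1 already does within arm. Leave the within-arm summaries and the mean ± SE plots as they are.

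The cost is a sentence or two in the SAP, a different procedure call and the sparse-strata rule. No new data are needed. Under SAP 4.8 the change should be documented before unblinding.

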### **9.5 Health-Related Quality of Life (HRQOL)**

The standardized measure of health status EQ-5D-5L will be used to provide a generic measure of health for clinical appraisal (Section 5.7.8). EQ-5D-5L includes six questions: mobility, self-care, usual activities, pain/discomfort, anxiety/depression, and global health score. The questionnaires will be self-completed by the subjects until disease progression.

Details of the planned analyses for these outcomes will be provided in the SAP

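### The EQ-VAS and EQ-Index mixed model has no treatment-by-visit term, so it returns one constant arm difference and cannot show how that difference changes over time

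*SAP*

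**What the plan says.** Protocol 9.5 leaves the HRQOL analyses to the SAP. SAP 7.5.1, under "Across treatment arms", plans for EQ-VAS and EQ-Index that "repeated-measures mixed-effects models will be used to explore treatment differences over time". The outcome is change from baseline, and the model has these parts:

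- Fixed effects: "The predictors (fixed effects) will be the baseline scores, treatment arms, visit, and randomization strata described in Section 2.5".
- Random effect: "The individual subject nested within the planned treatment arm will be the random effect".
- Output: "The estimated least squares means for the two treatment arm and their difference, the p-values comparing the 2 treatment arms and the effect size".

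The same section also plans by-visit work outside the model:

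- For each of the six questions at each time point: mean change within arm with its 95% CI, an effect size, the between-arm difference in effect sizes, and line plots showing both arms. It adds: "Difference in mean change from baseline for the questions at the time point will be evaluated by a two sample t-test".
- Protocol 9.5 makes clear that the sixth question is the global health scale: "EQ-5D-5L includes six questions: mobility, self-care, usual activities, pain/discomfort, anxiety/depression, and global health score".
- "For EQ-VAS and EQ-Index, descriptive statistics for change from baseline at each time will be presented", together with mean and mean-change plots by arm.

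The yardstick for size is: "An effect size greater than ≥ 0.3 will be considered potentially clinically meaningful". The model paragraph applies the same 0.3 mark to between-arm differences. SAP 7.5 classes all of this as exploratory and descriptive.

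**The concern.** The aim and the model do not match. A model with arm and visit as main effects only assumes that the two arms' mean profiles run parallel. It can say whether the arms differ on average. It cannot say whether the difference opens, closes or reverses as follow-up goes on, which is the stated aim.

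Timing matters for this endpoint. Protocol 1.4.2 gives time to deterioration as the HRQOL objective. Treatment is expected to last 3 to 5 months on average (Protocol 3.2), while questionnaires run every 4 weeks to Week 25 and every 8 weeks after that. Later visits will therefore contribute far fewer records than early ones, and a single pooled difference mostly reflects the early visits. This model is also the only longitudinal HRQOL comparison adjusted for baseline score and strata.

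**Working it through.** The plan gives no SD, effect, power or sample size for this model, so there is no stated figure to reproduce. The structural point follows from the formula. The sizes below are illustrations.

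**Step 1: what the model can express.** For a subject in arm a at visit j, the listed terms give

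E(change) = b × baseline + strata + arm_a + visit_j.

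Subtracting placebo from cabozantinib at the same visit, baseline and stratum leaves arm_cabo - arm_plac. There is no j in the result, so the fitted difference is identical at every visit. The random subject effect shifts a subject's whole profile and does not change this.

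**Step 2: how visits are weighted, by hand.** Assume exponential HRQOL follow-up with a mean of 4 months in both arms (an assumption). Four weeks is 28 days, and 28 / (4 × 30.4375) = 0.230, so the share remaining falls by a factor exp(-0.230) = 0.795 per visit. For Weeks 5, 9, 13, 17, 21 and 25 the shares are 0.795, 0.631, 0.502, 0.399, 0.317 and 0.252, summing to 2.896. The first three visits hold (0.795 + 0.631 + 0.502) / 2.896 = 67% of the records.

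Take a true difference of 0, -0.1, -0.2, -0.3, -0.4 and -0.5 SD at those visits:

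- Equal-weight average: -1.5 / 6 = -0.25.
- Record-weighted average: -(0.0631 + 0.1004 + 0.1197 + 0.1268 + 0.1260) / 2.896 = -0.185.

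The mixed model's weights are not exactly the record counts, so the second figure is an approximation.

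**Step 3: the same ramp, simulated.** Assumptions: 507 v 253 subjects, six visits, within-subject correlation 0.5, 15 to 25 trials per setting.

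| Mean follow-up, cabozantinib v placebo (months) | Model as in the SAP |
|---|---|
| 5 v 3 | -0.12 to -0.14 (three runs) |
| 4 v 4 | -0.17 |
| 8 v 6 | -0.16 |
| 8 v 8 | -0.19 |
| 12 v 12 | -0.21 |

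With so few trials, the ordering of the rows should not be read at the second decimal. With the interaction added, the Week 25 difference came out at -0.49 to -0.51 in the first three settings. Its equal-weight average, computed for 5 v 3 months, was -0.24. Without attrition, the SAP model and that average coincide.

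**Step 4: other shapes.** Here the visits run to Week 49, follow-up is exponential with median 3, 5 or 8 months and equal in both arms, strata are omitted, and there are 20 trials per case. Records from Week 25 onward made up 19%, 28% and 33% of the total.

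- No difference before Week 25, -0.5 SD from then on: the single estimate is -0.10, -0.13 and -0.15. As a rough check, 0.19 × 0.5 = 0.10, 0.28 × 0.5 = 0.14 and 0.33 × 0.5 = 0.17.
- +0.3 SD before Week 25, -0.5 SD from then on: +0.16, +0.11 and +0.07, the opposite sign to the late effect.
- In both cases the interaction model gives -0.55, -0.51 and -0.51 as the mean difference from Week 25.

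**The case against.** The strongest reply is that the model is only one part of the section and is introduced as an addition to by-visit summaries. A reader might infer that the plan as a whole would hide late worsening. The documents do not support that. A 0.5 SD gap at Week 25 on the VAS would appear in a t-test, an effect size and a plot. On EQ-Index it would appear in by-visit descriptive statistics and plots.

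A reader might also infer that the missing term is what pushes a real effect below the 0.3 mark. That compares an average with a single visit. In the ramp, even the equal-weight average is -0.25 and misses 0.3. Of the 0.38 between -0.50 at Week 25 and the lowest estimate of -0.12, 0.50 - 0.25 = 0.25 comes from averaging at all, and 0.25 - 0.12 = 0.13 from early-visit weighting under the assumed attrition.

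The attrition is itself uncertain. The 3 to 5 months in the protocol is time on treatment for all subjects and is not split by arm. Questionnaires continue after treatment stops, until the later of 8 weeks after progression or the decision to discontinue. Longer follow-up shrinks the understatement.

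A third tempting reading is that the model imposes equal correlation between visits and that this does damage. The SAP names a random subject effect and is silent on residual covariance. The simulations generated equally correlated data, so they show no such harm.

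What remains is narrower. The by-visit summaries are not adjusted for baseline score or strata and use only the subjects observed at each visit. No by-visit arm test is planned for EQ-Index. The one adjusted longitudinal comparison cannot address its stated aim.

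**Conclusion.** The point holds for the model, not for the HRQOL section as a whole. That the model gives a single constant difference is a fact of its specification and rests on no assumption. How far this understates a late difference depends on attrition and on the shape of the effect, neither of which the documents give. For a ramp to -0.5 SD by Week 25, the single estimate is roughly -0.12 to -0.21, against -0.25 for an equal-weight average. The SAP model therefore does not deliver a plain average over visits either, because its weights depend on who is still being assessed. The analysis is exploratory and descriptive, and OS, PFS and ORR testing is untouched. This is a worthwhile low-cost improvement, not a threat to the trial's conclusions.

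**What to change.** In SAP 7.5.1, for the EQ-VAS and EQ-Index model:

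- Add treatment-by-visit as a fixed effect, with visit categorical.
- Report least squares mean differences with 95% CIs at each visit, plus an average over visits with stated weights. Give effect sizes for both, so that it is clear which one is set against 0.3.
- Prespecify the within-subject covariance, with a simpler structure as fallback if the model does not converge.
- State the last visit included, or a rule for pooling sparse late visits.
- A baseline-by-visit term is optional.

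If the sponsor wants only an overall difference, the minimum change is to say so, state how visits are weighted, and drop the claim that the model examines differences over time.

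The cost is a short SAP edit before unblinding, for which SAP 4.8 provides. No new data are needed. The price is more parameters and wider intervals at late visits, which the fallback and the pooling rule are there to handle.
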